**Figure 1. Impact and anticipated future progression**

[figure not shown]
SWATSS = South Wales Adult Thoracic Surgical Service; WHSSC = Welsh Health Specialised Services Committee

### 1.3. Clinical Data

Analysis of our prospective data, which was published in the *Lancet* journal *EClinicalMedicine*, suggests that patients with dyspnoea, impaired PS, decreased LOA, frailty, and borderline or poor lung function can be optimized with a standardized Prehab program, allowing them to undergo curative lung surgery safely with acceptable frequency of PPC's, LOHS and mortality (15). Despite optimisation, there remain a section of patients who remain unfit for surgery or following surgery develop complications and experience longer stays in the high dependency unit and hospital (15).

[figure not shown]
There is emerging evidence that adding a hand-held Inspiratory Muscle Training (IMT) device (Figure 2) to Prehab further optimises surgical patients and improves post-surgical outcomes by reducing PPCs which results in shorter HLOS and reduces mortality (17-20). IMT improves the strength and endurance of inspiratory muscles, namely the diaphragm and intercostal muscles through a series of breathing exercises and greatly improves the ability of individuals to take in deep breaths following surgery and expectorate and clear their airway of retained secretions more effectively, which helps reduce PPCs (17-20). IMT is analogous to strengthening one's respiratory muscles with weightlifting and inspiratory muscles are able to work for longer duration (17-20). For this study we plan to use the POWERbreathe Medic IMT device which does have a CE mark. The device is not being used outside of the purposes for which it is CE marked for this research study. The POWERbreathe medic IMT device is evidence based for a variety of medical conditions such as chronic lung disease and thoracic surgery, and is currently used by multiple patient groups, including pre operative cardiac patients as part of routine care in the Health Board. The POWERbreathe medic IMT is a single patient use device that is not decontaminated and passed onto other patients to use after the study.

On the contrary, following lung resection, to manage pleural space complications of air leak, effusion and empyema, RCT-level evidence suggests that temporarily paralysing the diaphragm (an inspiratory muscle responsible for almost 80% of inspiratory effort) with cryo-neuro-ablation of the phrenic nerve, does not significantly prolong HLOS, PPCs and mortality (21).

**Figure 2. POWERBreathe Inspiratory Muscle Training Device**

In the presence of suggested equipoise, to obtain high level evidence for introducing IMT with Prehab into clinical practice for NSCLC surgical patients, we searched the Medline, Embase and the Cochrane library databases for English language RCTs, systematic reviews and meta-analyses published on “pulmonary rehabilitation” between Jan 1946 to May 2022 for “inspiratory muscle training”, “POWERbreathe Medic”, “inspiratory spirometry” (IS), “surgery”. Our search revealed 181 publications. 4 publications met the search question comparing IMT with Prehab and IS. Two RCTs were in cardiac surgery, one ‘pilot’ in upper gastro-intestinal surgery and one ‘pilot’ RCT in lung cancer surgery (Figure 3) (22-25).

**Figure 3. PRISMA flow diagram for a Systematic Review of Inspiratory Muscle Training (IMT) vs Standard Prehab**

The four RCTs, including the pilot RCT in lung cancer surgery, did not describe the impact of IMT on the quality of life (QoL) of patients who underwent surgery (22-25).

Whilst the four RCTs suggested that incorporating an IMT device to strengthen the diaphragm and muscles of inspiration improved pulmonary function prior to surgery, and following surgery reduced PPCs and HLOS, RCT level evidence evaluating the effectiveness of IMT in NSCLC surgical patients was graded low as the pilot RCT was underpowered (22) (12 patients in IMT group and 9 patients control group).

Lung resection patients commonly have COPD, reduced respiratory function, obesity, are on bronchodilators and develop PPCs. The RCT in cardiac surgical patients however, excluded these patients who are more likely to develop PPCs. Unlike abdominal and cardiac surgery, in lung cancer surgery a large volume of lung tissue is removed, which further compromises pulmonary function predisposing patients to increased PPCs, mortality, HLOS and impacts QoL. As cardiac and abdominal surgical patients do not reflect the thoracic surgical population as lung tissue is not removed at surgery in these patient populations. Hence, it is not possible to extrapolate their RCT evidence to lung resection patients (21-25)

Additionally, there is significant research with IMT in the intensive care population (26), however these results cannot be generalised to our population of patients for lung resection surgery. Whilst there are similarities between the two patient groups, such as chronic respiratory conditions and deconditioning, patients can suffer other intensive care related conditions such as critical illness polyneuropathy from sepsis. Additionally, outcome measures between the two patient populations differ.

#### **1.4. Rationale and Risks/Benefits**

We hypothesise that prior to surgery, an IMT device in combination with a standard Prehab program compared with Prehab alone, will further improve the strength and endurance of the surgical NSCLC patients' inspiratory muscles used for breathing. By doing so, IMT with Prehab will allow patients who have undergone lung resection surgery to clear their airway of secretions more effectively in the post-operative period and provide a significant benefit to patients by lowering their risk of developing PPCs and shorten their HLOS after surgery, improve their overall QoL and additionally reduce NHS costs.

There are no expected risks to participants of this trial. Our previous studies, have shown that thoracic Prehab safely optimises patients for surgery (14,15). Good tolerance with IMT devices have been reported, although can cause feelings of fatigue (27,28).

---

## 2. Objectives and Design

### 2.1. Trial Objectives

**Primary Objective:** A randomised controlled trial to evaluate the impact of thoracic PRehabilitation with Inspiratory Muscle tRaining cOmpared to Standard prEhabilitation in surgical lung cancer patients [PRIMROSE Trial].

**Recruitment rate:** The study aims to recruit 134 patients for randomisation over twelve months, with 67 randomised to the intervention group and 67 to the control group (6).

**Retention rate:** These are high-risk patients and a high attrition rate in this population is considered normal. We anticipate the retention of 50 patients in each arm following 1:1 randomisation, and is based on our previous study (15), which showed that following assessment, 6.8% NSCLC patients fail to attend Prehab and 1.1% died prior to commencing Prehab. Likewise, following Prehab, 75.8% patients are ready to proceed with surgery. The attrition rate is an estimate and is anticipated attrition to be 20%-25%.

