## 1. Introduction

### 1.1. Background

Lung cancer is the most common cause of cancer-related deaths in Wales (1). Although surgical resection for early-stage lung cancer with curative intent remains the primary treatment, patients with significant smoking related underlying cardiopulmonary disease and impaired pulmonary function, dyspnoea, frailty and decreased activity levels are unfit for surgery and referred for alternative treatment (2,3). Secondly, individuals who proceed to lung resection, thoracic surgery and general anaesthesia may have direct effects on their respiratory system potentially leading to postoperative pulmonary complications (PPCs), which increases hospital morbidity, prolongs hospital length of stay (HLOS) impacts on the quality of life (QOL) of patients and adds to health-care costs (4). Our aim is to evaluate whether incorporating a breathing training device, POWERBreathe into the existing standardised thoracic prehabilitation program (Prehab) will optimise unfit patients physically for surgery, and following surgery reduce their risk of developing PPC's, reduce HLOS and improve QOL of patients and improve service outcomes (5).

The PRIMROSE study aims to compare two groups of patients referred for Prehab who have lung cancer treatable with surgery: (A) standard Prehab and training with the inspiratory muscle training (IMT) device; and (B) standard Prehab alone, in non-small cell lung cancer patients (NSCLC) undergoing lung resection surgery, with clear primary and secondary outcome measures.

One hundred and thirty-four patients will be recruited for the study (67 for each arm) and with an anticipated attrition rate of 25%, one hundred patients will finally be studied (6,7). With 134 recruited and an attrition rate of 25%, only 100 will remain (50 in each arm). The primary outcome measure tested will be the proportion of patients in each group experiencing postoperative pulmonary complications (PPC), which will be graded I-V using the Clavien Dindo Classification (8). PPCs will be broadly classified as minor (grade 1) and major complications (grade 2-5 where 5 is death). What we want to learn from this RCT study is whether IMT helps reduce grade  $\geq 2$  PPCs to either grade 1 or no complications and thereby help shorten the length of stay in hospital for patients undergoing lung resection surgery.

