**Post-discharge assessment:** Our primary objective is to determine whether IMT prior to surgery with Prehab helps reduce PPC following surgery, which is up to the point of discharge from hospital (alive or dead). This is one time point. Hence, it is anticipated that all patients will complete the discharge assessment for complications. Thus, the study is not underpowered for the primary end point.

Mortality rates will be collected at discharge, 1 month, 3 months, and 365 days post-surgery.

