### 3.3. Exclusion Criteria:

- Inclusion criteria not met
- Patients who have undergone recent abdominal surgery and those with an abdominal hernia
- Patients diagnosed with other cancers namely, patients with metastatic lung cancer, mesothelioma, sarcoma, mediastinal tumours, or benign diseases
- Patients who decline Prehab
- Patients who do not consent to Prehab, do not attend or have died prior to commencing Prehab. Patients who do not consent to surgery.
- Patients with a high cardiovascular risk for Prehab and awaiting investigations or interventions (including unstable angina and syncope)
- Patients with a serious concomitant disorder that would compromise patient safety during Prehab
- Patients with a history of spontaneous pneumothorax and/or evidence of large bullae on radiological imaging
- Patients who have suffered from or likely to suffer from costochondritis
- Patients with marked osteoporosis with history of rib fractures
- Patients with pulmonary hypertension
- Patient with a perforated ear drum
- If a participant is involved in a study similar, with potential to cause bias or conflict of interest then they will be excluded
- Patients with worsening heart failure signs and symptoms after IMT

To prevent the transmission of respiratory infections, the research team will advise patients not to share the device with family members. If patients are suffering from a cold, sinusitis or respiratory tract infection they will be advised not to use the device until their symptoms have resolved.

Participants who do not understand written and/or spoken English can access a translator through the health board.

The research team will collect a list of patients that decline to participate in the trial, to assess recruitment rates at the end of the study.

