### **9.8. Non-Compliance**

Patients who do not adhere to the proposed intervention will be offered a telephone consultation, to consider behaviours and characteristics, preferences, barriers and facilitators to enable and explore compliance. This could be done with the carer if the patient wishes. If adherence remains an issue patients will be removed from the research and will be asked to return their patient diary for analysis.

A noted systematic lack of both the CI and the study staff adhering to SOPs/protocol/ICH-GCP, which leads to prolonged collection of deviations, breaches or suspected fraud.

These non-compliances may be captured from a variety of different sources including monitoring visits, CRFs, communications and updates. The sponsor will maintain a log of the non-compliances to ascertain if there are any trends developing which to be escalated. The sponsor will assess the non-compliances and action a timeframe in which they need to be dealt with. Each action will be given a different timeframe dependent on the severity. If the actions are not dealt with accordingly, the research and development Office will agree an appropriate action, including an on-site audit.

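### The 20–25% attrition figure does not follow from the losses Section 2.1 cites for it: depending on two points the protocol leaves open, 134 recruits leave about 94 or about 102, and Section 9.8 removals are not budgeted

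*Protocol*

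**What the plan says.** Section 2.1 sets the target: "The study aims to recruit 134 patients for randomisation over twelve months, with 67 randomised to the intervention group and 67 to the control group". Under retention rate it anticipates 50 patients per arm after 1:1 randomisation and attributes this to the previous study, with losses at two stages. After assessment, "6.8% NSCLC patients fail to attend Prehab and 1.1% died prior to commencing Prehab". Then: "Likewise, following Prehab, 75.8% patients are ready to proceed with surgery". The paragraph ends with an estimated attrition of 20–25%. Section 1.1 turns the upper end into the sample size: "With 134 recruited and an attrition rate of 25%, only 100 will remain (50 in each arm").

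Five other places bear on this:

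- Section 3.3 lists among the exclusions "Patients who do not consent to Prehab, do not attend or have died prior to commencing Prehab".
- Section 4.3 gives the allocation ratio and the service used, but does not place randomisation relative to the start of Prehab.
- Section 2.4.1, under post-discharge assessment, reasons that complications are assessed at a single time point, discharge, and concludes: "Thus, the study is not underpowered for the primary end point".
- Section 9.8 offers non-adherent patients a telephone consultation and continues: "If adherence remains an issue patients will be removed from the research".
- Section 4.12 says every patient enters the final analysis by intention to treat, including those who withdraw or are withdrawn.

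**The concern.** The retention paragraph names two losses as its basis, but the attrition it states is the size of the second alone: 100% − 75.8% = 24.2%. The 7.9% lost before Prehab is cited and does not appear to be deducted. If it belongs in the calculation, 134 recruits do not leave 100. If it does not, it should not be offered as a basis for retention after randomisation. Either way, a reader cannot get from the cited figures to 20–25% without an assumption that the protocol does not state.

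The 100 analysed patients carry the 80% power statement, and 134 leaves no cushion even when everything goes as planned. Section 9.8 adds a further loss after randomisation. Removal for non-adherence is selective, and it may fall unevenly because the intervention arm has an additional twice-daily regimen to adhere to. It can therefore bias the comparison as well as shrink it.

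**Working it through.** **Inputs.** 134 recruits (67 per arm), attrition 20–25%, pre-Prehab losses of 6.8% and 1.1%, and 75.8% ready for surgery (Sections 1.1 and 2.1). Control-arm complication rate 36.7%, 80% power, 50 per arm (Section 2.4.1). Significance level 0.05, two-sided (Section 2.4.2).

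**The plan's own figure.** 100 / (1 − 0.25) = 133.3, rounded up to 134, and 134 × 0.75 = 100.5. The stated figure is reproduced, with a margin of half a patient.

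**Reading A: losses sequential, both after randomisation.**
- Pre-Prehab loss: 6.8% + 1.1% = 7.9%, so 92.1% start Prehab.
- Retention: 0.921 × 0.758 = 0.698, so attrition is 30.2%.
- Remaining: 134 × 0.698 = 93.5, about 94 (47 per arm).
- Recruits needed to leave 100: 100 / 0.698 = 143.2, so 144 (72 per arm).

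**Reading B: the 7.9% is lost before randomisation, or 75.8% is a share of all assessed patients.**
- Attrition: 24.2%, inside the stated range.
- Remaining: 134 × 0.758 = 101.6, about 102 (51 per arm). The target is met with fewer than two patients to spare.

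**Power.** The intervention-arm rate is not in the readable text (the calculator output in Figure 5 is not shown), so it has to be assumed. Solving for the rate that gives 50 per arm at 36.7%, two-sided 0.05 and 80% power yields about 13.3% with the unpooled formula, about 12.7% with the pooled formula and about 11% with a continuity correction. As a check on the first: 7.849 × (0.367 × 0.633 + 0.133 × 0.867) / 0.234² = 49.8, so 50. Exact power of the uncorrected chi-square test:

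| Assumed intervention rate | 50 per arm | 47 per arm | Loss |
|---|---|---|---|
| 13.3% | 79% | 76% | about 3 points |
| 12.7% | 82% | 79% | about 3 points |
| 11% | 88% | 86% | about 2 points |

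The loss is 2–3 points across the range. Whether power ends above or below 80% depends on the unseen rate.

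**What the reassurance in Section 2.4.1 covers.** Its argument is that everyone can be assessed by discharge. That addresses missing outcomes among patients who have surgery. The losses in Section 2.1 occur before surgery, so the argument does not reach them.

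**Section 9.8 against Section 4.12.** One removes persistent non-adherers from the research; the other analyses everyone, including those withdrawn. Without further data collection, a removed patient has no primary outcome to analyse. None of the cited attrition figures includes this loss, and on Reading B two such removals take the number below 100.

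**The case against.** The best defence is that the shortfall needs two premises the protocol does not fix. First, the denominator of 75.8% is not given; if it is all assessed patients, 24.2% is already the total loss. Second, Section 3.3 excludes people who do not attend or who die before starting Prehab, which points to the 7.9% falling outside the randomised set. Consent is not randomisation, and Section 4.1 asks for at least 24 hours between information and consent, so randomisation may well come later than the first assessment. This stands. A reader might infer that attrition is simply wrong at 20–25% and that 50 per arm will not be reached. The documents do not support that as fact, because Reading B meets the plan. What the defence does not explain is why Section 2.1 then cites the 7.9% in support of retention after randomisation.

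A second tempting inference starts from the 80% adherence anticipated in Section 2.1 and removes a further 20%, leaving about 75 (93.5 × 0.8) or 81 (101.6 × 0.8). That is at most an upper bound. Anticipated non-adherence is not anticipated removal, Section 9.8 tries a consultation first, and non-adherers may overlap with those who never reach surgery.

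It is also fair to say that the Section 2.4.1 sentence is about outcome ascertainment. Read that way it is reasonable, but its wording makes a general claim about power.

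**Conclusion.** The point holds in a conditional form. The stated basis does not yield 20–25% unless the 7.9% falls before randomisation or 75.8% already includes it, and the protocol says neither. If the losses are sequential and after randomisation, attrition is about 30%, about 94 patients remain, and power is 2–3 points below its value at 50 per arm. Otherwise about 102 remain and the target is met with almost no reserve.

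The power cost of compounding alone is modest. It does not justify calling the trial seriously underpowered, and at an assumed intervention rate of 11% power stays above 80% even with 47 per arm. The conflict between Sections 9.8 and 4.12 does not depend on which reading is right, and it matters more for bias than for numbers.

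**What to change.** 1. In Section 2.1, state the denominator of 75.8% and show how the attrition figure follows. In Section 4.3, state that randomisation takes place once the participant attends to start Prehab, so that the 7.9% falls before it. If randomisation is to stay earlier and the losses are sequential, restate attrition as about 30%, the expected analysed number as about 94, and the correspondingly lower power from the calculator's own inputs.
2. In Section 2.4.1, limit the statement about not being underpowered to outcome ascertainment after surgery.
3. Reconcile Section 9.8 with Section 4.12 so that non-adherent participants who have not withdrawn consent stay in outcome follow-up and in the intention-to-treat analysis. This concerns data collection and analysis only; it sets no rule on continuing or stopping treatment.

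The cost is protocol wording. No extra patients are needed unless the sponsor finds that Reading A applies and still wants 100 analysed, which would take about 144 recruits.

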#### Secondary Objectives:

**Adherence to trial procedures:** It is anticipated that 80% of participants will adhere to the study protocol.

**Collection of participant outcome data and completion rate:** It is anticipated that all data on each of the individual participants at each time point in each arm of the study will be accurately and contemporaneously collected by the research team. The percentage of patients in whom all data sets at each time point is accurately and contemporaneously obtained will describe the data completion rate, which is an anticipated >95%.

**Follow-up:** Following surgery, >80% are expected to successfully complete the post-discharge assessments. We anticipate a >80% follow-up assessment.

[figure not shown]
## 2.2. Trial Design:

This is a randomised controlled PRIMROSE trial. This trial will be single centred, as there are very few centres in the United Kingdom (UK) that deliver this highly specialised service.

Study population: Lung cancer patients with surgically resectable disease referred for pre-treatment optimization with Prehab, from the lung cancer Multi-Disciplinary Teams (MDT's) across South West Wales. Eligible patients will be randomised to the trial on a 1:1 ratio to either the intervention arm or control arm [figure 4].

Participants in group A will receive standard Prehab and training with the IMT device (POWERBreathe); participants in group B will receive standard Prehab alone.

## 2.3. Figure 4. Study Scheme Diagram:

**Figure 4. Consolidated standards of reporting trials (CONSORT) diagram for the PRIMROSE Trial**

[figure not shown]
6MWD= 6 minute walk distance test; cf. = compared with; CTM UHB = Cwm Taf University Health Board; FEV1= Forced expiratory volume in 1 second; ; Hdd = Hywel Dda Health Board; IMT= Inspiratory muscle training; LOA = level of activity; HLOS = Hospital length of stay; PPCs = post-operative pulmonary complications; PS= performance status; TLCO= transfer factor; QLQ= quality of life questionnaire;

To ensure the effectiveness of our study protocol, we have utilised the principles of the UK Medical Research Council guidance framework for developing and evaluating complex interventions pilot and feasibility studies (6,7).

## 2.4. Statistical Methodology and Analysis

### 2.4.1. Sample size, justification and calculations

Our literature search did not bring up a suitable RCTs on the use of POWERBreathe Inspiratory Muscle Trainer (IMT) in lung resection patients. Hence, we used the outcome data from the RCT on cardiac patients on whom POWERBreathe IMT was used and we have experience with. We acknowledge that the cardiac surgery patient population are very different and do not accurately reflect our study population (as patients undergoing cardiac surgery do not undergo lung resection). There is one RCT on the use of inspiratory spirometry used in patients undergoing lung resection in order to strengthen their diaphragm function prior to surgery (29). Inspiratory muscle training using inspiratory spirometry is different to the POWERBreathe IMT. However, the patient population and design of this RCT are more in line with our PRIMROSE Trial, making it more pertinent to use the data from this RCT instead of the RCT in a cardiac population. Hence, using the data from the lung resection patient trial, and assuming a 36.7% incidence of PPC after surgery in the control arm and using a significance level of 0.05 and a power of 80%, the online calculator estimates 50 patients are required in each arm of the study (Figure 5).

